# **Statement of Compliance**

This study will be conducted in accordance with the Code of Federal Regulations on the Protection of Human Subjects (45 CFR Part 46), 21 CFR Parts 50, 56, 312, and 812 as applicable, any other applicable US government research regulations, and institutional research policies and procedures. The International Conference on Harmonisation ("ICH") Guideline for Good Clinical Practice ("GCP") (sometimes referred to as "ICH-GCP" or "E6") will be applied only to the extent that it is compatible with FDA and DHHS regulations. The Principal Investigator will assure that no deviation from, or changes to the protocol will take place without prior agreement from the sponsor and documented approval from the Institutional Review Board (IRB), except where necessary to eliminate an immediate hazard(s) to the trial participants. All personnel involved in the conduct of this study have completed Human Subjects Protection Training.

### **List of Abbreviations**

ΑE Adverse Event/Adverse Experience

CFR Code of Federal Regulations

CRF Case Report Form

CSOC Clinical Study Oversight Committee

DCC **Data Coordinating Center** 

DHHS Department of Health and Human Services

DSMB Data and Safety Monitoring Board

FFR Federal Financial Report FWA Federalwide Assurance GCP Good Clinical Practice

HIPAA Health Insurance Portability and Accountability Act

**ICF** Informed Consent Form

ICH International Conference on Harmonisation

IRB Institutional Review Board ISM Independent Safety Monitor

MOP Manual of Procedures

Ν Number (typically refers to participants)

NIH National Institutes of Health

OHRP Office for Human Research Protections OHSR Office of Human Subjects Research

Ы Principal Investigator QΑ Quality Assurance QC **Quality Control** 

SAE Serious Adverse Event/Serious Adverse Experience

SOP Standard Operating Procedure

US **United States**  Study number: i20-00356 Page 7
Version: June 8, 2020

# **Protocol Summary**

Title	A Comparative Study Evaluating the Diagnostic Accuracy of Wrist Arthroscopy Using the NanoScope Compared to Conventional Arthroscopic Instrumentation
Short Title	Wrist Arthroscopy Study
Brief Summary	The purpose of this study is to evaluate the diagnostic efficacy of Arthrex NanoScope compared to conventional arthroscopic instruments. Patients with wrist pathology who are indicated for an arthroscopic procedure will be enrolled pre-operatively after a thorough discussion of the study aims, risks, and benefits. At the time of surgery, under standard conditions, using standard wrist arthroscopy portals, a diagnostic arthroscopy will be performed with the Arthrex Nanoscope. The diagnostic arthroscopy will be performed in a stepwise manner for consistency with notation of pathology and intended intervention. The diagnostic arthroscopy will then be performed with the standard arthroscopic equipment, again noting pathology and final intervention. Post-operatively, diagnostic accuracy, incidence of change in intervention, and surgeon rated ease of use and confidence will be determined.
Phase	Not applicable
Objectives	Primary Outcome: To compare the diagnostic sensitivity and specificity of the NanoScope compared to conventional arthroscopic instruments.  Secondary Outcome: To determine if the diagnostic variability between NanoScope and conventional arthroscopic instruments results in a change in intervention. Surgeon-rated ease of use. Surgeon-rated diagnostic confidence.  Secondary Outcome: To determine the diagnostic correlation between preoperative MRI and arthroscopy (NanoScope and conventional).
Methodology	Prospective Cohort Study, Diagnostic

Study number: i20-00356 Version: June 8, 2020

[figure not shown]
Primary	Primary  1. Diagnostic accuracy of Nanoscope compared to conventional arthroscope.  Secondary  1. Incidence of change in intervention.  2. Surgeon rated ease of use.  3. Surgeon rated confidence of diagnosis.
21.1.2.11	4. Comparative correlation between pre-operative MRI and arthroscopy.
Study Duration	1 year
Participant Duration	1 day
Duration of IP administration	Not applicable
Population	N = 34, men and women, age ≥ 18 years, being treated at NYU Langone Health
Study Sites	
 
NYU Langone Orthopedic Hospital
 
Tisch Hospital, NYU Langone Health
 
NYU Langone Orthopedic Center (38th Street)
 
Joan H. & Preston Robert Tisch Center at Essex Crossing, NYU Langone Health
 

Number of participants	34
Description of Study Agent/Procedure	The Arthrex NanoScope is a 1.9 mm wrist arthroscopy system.
Reference Therapy	Conventional wrist arthroscope
Key Procedures	Diagnostic wrist arthroscopy of wrists with clinical and imaging confirmation of internal derangement (ligament/articular/bony injury).
Statistical Analysis	Descriptive statistics will be used to provide a quantitative summary of the data in the study. Specifically, the analysis performed included measures of central tendency (mean, median, and mode) and measures of variability (range and standard deviation). Categorical data will be described in percentages and a Chi-squared test will be employed to detect if these categorical variables are related between the two treatment groups with a p value of < .05. Continuous data will be described in means with standard deviations. A two-tailed Student's T-test will be employed to compare the means between the two treatment groups with a p value of < .05.

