### Final Assessments:

- 1. Compare diagnostic accuracy of NanoScope compared to conventional wrist arthroscopy instruments (gold standard).
  - a. Sensitivity
  - b. Specificity
- 2. Determine the rate of change in intervention.
- 3. Characterize surgeon-rated ease of use and surgeon-rated diagnostic confidence.
- 4. Determine the diagnostic correlation between pre-operative MRI and arthroscopy (NanoScope and conventional).

ept as authorized in writing by the study sponsor

Th Intervention

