# 3 Objectives and Purpose

# 3.1 Primary Objective

To evaluate the diagnostic accuracy of the Arthrex NanoScope compared to conventional arthroscopic instruments.

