### 4.2 Study Endpoints

### 4.2.1 Primary Study Endpoints

The primary endpoint will be diagnostic accuracy (%) compared to the gold standard of conventional wrist arthroscopy instruments.

The primary endpoint was chosen to determine if smaller instrumentation provides adequate visualization for the diagnosis of wrist pathology and can therefore be used as the sole means of evaluation.

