# 7.1 Study Procedures/Evaluations

### 7.1.1 Study Specific Procedures

- Patients undergoing wrist arthroscopy for diagnostic evaluation and treatment of a wrist injury will be enrolled pre-operatively following a
  discussion of the study, risks, benefits, and informed consent.
- All patients will be positioned supine and placed in an upper extremity traction tower with the shoulder abducted, elbow flexed to 90 degrees, forearm in neutral position.
- Standard arthroscopic portals will be made for viewing, instrumentation, inflow, and outflow: 3-4 portal, 6-R portal, midcarpal ulnar (MCU) portal, +/- midcarpal radial (MCR) portal, +/- 6-U portal.
- A diagnostic arthroscopy will be performed with the Arthrex NanoScope.
  - Structures evaluated:
    - Radial styloid
    - Proximal scaphoid articular cartilage
    - Scaphoid fossa
    - Radioscaphocapitate (RSC) ligament
    - Long radiolunate (LRL) ligament
    - Short radiolunate (SRL) ligament
    - Scapholunate (SL) ligament
    - Proximal lunate articular cartilage
    - Lunate fossa
    - Triangular fibrocartilage complex (TFCC)
  - The attending performing the diagnostic arthroscopy will make an initial diagnostic assessment based on the presence/location/severity of synovitis, articular cartilage integrity, ligament injury and determine the intended treatment.
- A diagnostic arthroscopy will then be performed with the standard arthroscopic instruments.
  - Structures evaluated:
    - Radial styloid
    - Proximal scaphoid articular cartilage
    - Scaphoid fossa
    - Radioscaphocapitate (RSC) ligament
    - Long radiolunate (LRL) ligament
    - Short radiolunate (SRL) ligament
    - Scapholunate (SL) ligament
    - Proximal lunate articular cartilage
    - Lunate fossa
    - Triangular fibrocartilage complex (TFCC)
  - The attending performing the diagnostic arthroscopy will make the final diagnostic assessment based on the presence/location/severity of synovitis, articular cartilage integrity, and ligament injury and determine the final treatment.

Study number: i20-00356 Page 17 Version: June 8, 2020

- Following the procedure the surgeon will perform a short questionnaire.
  - Surgeon rated visualization. (5 point scale)
  - Surgeon-rated ease of use. (5 point scale)
  - o Surgeon-rated diagnostic confidence. (5 point scale)
- The initial diagnostic assessment and final diagnostic assessment will be compared to determine diagnostic accuracy of the Arthrex NanoScope.

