- "Intended" treatment and "final" treatment will be compared to determine if diagnostic variability would result in potential treatment variability.
- Patients with pre-operative MRIs with a corresponding radiology report will be compared to arthroscopic findings to determination correlation between MRI and arthroscopy.
- No follow-up is required for the purposes of this study.

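### The primary outcome is announced as sensitivity and specificity, but the endpoint and analysis sections give one accuracy percentage and define no positive finding, matching rule or scoring unit

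*Combined protocol and SAP*

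**What the plan says.** **The primary quantity.** The objectives in the Protocol Summary give the primary outcome as "To compare the diagnostic sensitivity and specificity of the NanoScope compared to conventional arthroscopic instruments"; the endpoint list in the same summary says diagnostic accuracy. The Final Assessments list in the Schematic reads "Compare diagnostic accuracy of NanoScope compared to conventional wrist arthroscopy instruments (gold standard)" and has sensitivity and specificity as its two sub-items. Section 3.1 is general: "To evaluate the diagnostic accuracy of the Arthrex NanoScope compared to conventional arthroscopic instruments". Section 4.2.1 is narrower: "The primary endpoint will be diagnostic accuracy (%) compared to the gold standard of conventional wrist arthroscopy instruments". Section 10.3.2 describes accuracy as an incidence or percentage against the conventional-scope diagnosis. It names neither sensitivity nor specificity and provides no confidence interval.

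**What is recorded and compared.** Section 7.1.1 lists the same ten structures for each scope and bases each assessment on "presence/location/severity of synovitis, articular cartilage integrity, ligament injury". It continues: "The initial diagnostic assessment and final diagnostic assessment will be compared to determine diagnostic accuracy of the Arthrex NanoScope". Separately, the intended and final "treatment will be compared to determine if diagnostic variability would result in potential treatment variability".

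**The sizing.** Section 10.4 contrasts a sensitivity of 0.70 (attributed to MRI) with 0.90 (attributed to arthroscopy) at 90% prevalence, and asks for at least 34 subjects, at least 31 of them with a ligament injury. The Key Procedures entry in the summary uses a wider condition: "Diagnostic wrist arthroscopy of wrists with clinical and imaging confirmation of internal derangement (ligament/articular/bony injury)".

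**The SAP.** Section 10.1 defers a formal SAP to some point before database lock.

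**The concern.** Sensitivity and specificity need a 2x2 table, and that table needs a defined unit and a rule for calling a finding positive. The plan has neither. Section 10.3.2, followed to the letter, yields one percentage, and the two measures named in the Summary and Schematic cannot be recovered from it.

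The choice matters because section 4.2.1 wants to know whether the smaller scope could be relied on alone. That depends both on injuries missed and on injuries called that are not there. Over-calls that change the planned treatment would appear in the secondary endpoint on change of intervention; others would appear only if the primary analysis is built to show them.

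Timing also matters. The study is unblinded (section 10.5.2), and the SAP may come after all cases are done. A unit fixed that late is weaker evidence than one fixed in advance.

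**Working it through.** **1. Reproduce the sizing, to see what it counts.** Inputs from section 10.4: null sensitivity 0.70, alternative 0.90, 90% prevalence. Exact two-sided binomial test of one proportion in n = 31, rejecting at 16 or fewer or at 27 or more positives:
- Attained alpha = 0.0239 + 0.0239 = 0.0478 (table row: 0.048).
- Power at 0.90 = 0.8068 (table row: 0.807).
- N = 31/0.90 = 34.4, printed as 34.

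So the sizing counts patients, with ligament injury as the condition. The text's power of 0.819 belongs to the 0.80 versus 0.90 row (N1 = 107, N = 119). That is a separate matter.

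**2. If scored as injured or not per wrist.** Negatives = 34 - 31 = 3 at most when the 31-injured minimum is met; expected number at 90% prevalence = 34 x 0.10 = 3.4. Exact (Clopper-Pearson) 95% intervals:

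| Measure | Count | 95% CI |
|---|---|---|
| Specificity | 3/3 | 29% to 100% |
| Specificity | 2/3 | 9% to 99% |
| Specificity, more negatives than planned | 6/6 | 54% to 100% |
| Sensitivity | 28/31 | 74% to 98% |

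Six is a generous case: with 34 independent wrists at 90% prevalence, the chance of 6 or fewer negatives is 95%.

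Overall accuracy barely registers specificity here. With sensitivity 0.90 in 31 wrists, accuracy = (31 x 0.90 + 3 x specificity)/34, which runs from 27.9/34 = 82% at specificity 0 to 30.9/34 = 91% at specificity 1. Calling every wrist injured gives 31/34 = 91%.

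**3. If scored as agreement on the complete diagnosis.** A miss and an over-call each make a wrist discordant. Both lower the percentage, but the percentage does not say which occurred.

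**4. If scored per structure.** There are 34 x 10 = 340 calls, clustered ten to a wrist. The documents give no abnormal rate or within-wrist correlation (ICC), so precision can only be illustrated. Assume 10% abnormal (34 abnormal calls) and a true sensitivity of 0.90. On the logit scale the centre is ln(0.9/0.1) = 2.197 and SE = 1/sqrt(n x 0.9 x 0.1).
- ICC 0: n = 34, SE = 0.572, limits 75% to 97%.
- ICC 0.3 with the pessimistic design effect 1 + 9 x 0.3 = 3.7: n = 34/3.7 = 9.2, SE = 1.10, limits 51% to 99%.

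**5. How far the unit alone can move the result.** A constructed case, not a forecast: the scopes disagree on 17 of 340 structure calls, one in each of 17 wrists that also have another injury seen on both scopes.
- Structure level: 323/340 = 95%.
- Complete diagnosis: 17/34 = 50% (exact 95% CI 32% to 68%).
- Injured or not: 34/34 = 100% (90% to 100%).

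Nothing in the plan rules out any of the three.

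**The case against.** The best defence is that the statements fit together. The Schematic puts sensitivity and specificity under diagnostic accuracy, section 3.1 is compatible with that, and sizing on one component does not create another endpoint. This stands: a reader might infer three rival primary endpoints, or that section 3.1 commits to a percentage, and the documents support neither. What remains is that the two governing sections, 4.2.1 and 10.3.2, carry only the percentage.

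The second defence is that sections 7.1.1 and 10.3.2 read most naturally as diagnosis against diagnosis, so over-calls are penalised. That is fair. It confines the 3-wrist result to binary per-wrist scoring, which no endpoint section adopts. But it supplies no matching rule and does not yield sensitivity or specificity.

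Other stronger readings also go too far:
- That the study is underpowered for specificity. No specificity test or target is set, so the issue is estimation only.
- That the wider injury definition in Key Procedures leaves still fewer negatives. It describes pre-operative confirmation, not the arthroscopic reference result. A wider definition cannot add negatives, but whether it removes any is not derivable.
- That structure-level findings will go unrecorded. The Summary promises that pathology will be noted with each scope, and no case report form is in the documents.
- That the unit will be picked after results are seen. The plan leaves this open; it does not say so.

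**Conclusion.** The concern holds as a gap in definition and alignment that should be fixed. The promised sensitivity and specificity do not follow from the analysis in section 10.3.2, and no section supplies the positive finding, the matching rule or the unit.

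Its size depends on the unit eventually chosen. Under binary per-wrist scoring, specificity would rest on about 3 wrists and be uninformative. Under complete-diagnosis agreement, the percentage would be meaningful but would merge misses with over-calls. Under structure-level scoring, both measures could be estimated, with a precision that the documents do not allow anyone to predict.

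The per-wrist figures rest on section 10.4's own 31 of 34 and 90% prevalence. The structure-level limits rest on an assumed abnormal rate, ICC and true value.

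**What to change.** Before enrolment:
- Define the positive finding (including the threshold for abnormal), whether location and severity must match, and the unit. Put one primary statement in the Protocol Summary, Schematic and sections 4.2.1, 10.3.2 and 10.4.
- Record normal or abnormal on each scope for each of the ten structures in section 7.1.1, with synovitis as its own item.
- Report the structure-level 2x2 table with sensitivity, specificity and patient-clustered 95% CIs, with counts per structure. Alongside it, report patient-level agreement on the complete diagnosis with an exact CI, which speaks directly to the question in section 4.2.1 of using the scope alone. The sponsor names in advance which is primary.
- Report wrist-level specificity only as a count with its exact CI.
- If no errors occur, clustered intervals collapse. Use an exact CI on the number of patients who contribute to that measure. For sensitivity this may be fewer than 34: at 10% abnormal with independent structures, about 34 x (1 - 0.9^10) = 22 wrists, and 22/22 has a lower limit of 85%.
- State that N = 34 was sized for sensitivity 0.70 versus 0.90, and not for specificity or structure-level precision.

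Cost: no extra patients or procedures; changes of wording, a recording grid if none exists, slightly more recording in theatre, and a clustered analysis. The sponsor should accept in advance that structure-level sensitivity may be imprecise if few structures are abnormal.

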### 3.2 Secondary Objectives (if applicable)

To determine if the diagnostic accuracy of the Arthrex NanoScope compared to conventional arthroscopic instruments results in a change in intended intervention.

To determine the surgeon-rated ease of use and diagnostic confidence of the Arthrex NanoScope.

To determine the diagnostic correlation between pre-operative MRI and arthroscopy (NanoScope and conventional). The MRI is standard of care for evaluation of ligamentous wrist pathology. It will not be mandated as part of the protocol.

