# 5 Study Enrollment and Withdrawal

### 5.1 Inclusion Criteria

In order to be eligible to participate in this study, an individual must meet all of the following criteria:

- 1. Age > 18 years.
- 2. Wrist pathology based on clinical examination/imaging studies undergoing wrist arthroscopy for further evaluation/treatment.
- 3. Willingness to participate in the study

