### 5.4 Strategies for Recruitment and Retention

Patients will be recruited from investigator clinical practices. The recruitment plan does not propose to use any NYULMC media services or social media. Patients with clinically diagnosed wrist pathology undergoing wrist arthroscopy will be identified by the attending physician and recruited for the study in the office visit when surgery is indicated/scheduled or in the pre-operative area on the day of surgery. The nature of the information the subjects will be asked to give about themselves will include objective information relevant to their wrist injury. Only the individuals listed in the protocol will have access to the patients study.

As this study does not require long-term patient participation, there are no relevant modalities necessary to enhance participant retention.

The target sample size is 34 patients, recruited from the investigators clinical practice.

Study number: i20-00356 Page 14 Version: June 8, 2020

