### 10.3.3 Analysis of the Secondary Endpoint(s)

### Secondary

- 1. Incidence of change in intervention.
- 2. Surgeon rated ease of use.
- 3. Surgeon rated confidence of diagnosis.
- 4. Correlation between pre-operative MRI findings and arthroscopic findings.

Secondary endpoints will be described using incidence/percentage. A two-tailed Student's T-tests will be employed to compare the means of surgeon-rated outcomes between the Arthrex NanoScrope and conventional instruments groups with a p value of .05.

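### MRI-versus-arthroscopy agreement is measured only in operated wrists, with entry described three ways, so a percentage summary is inflated by selection and should be analysed by structure

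*Combined protocol and SAP*

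**What the plan says.** The entry population is described in three places:

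- Protocol Summary, Key Procedures: "Diagnostic wrist arthroscopy of wrists with clinical and imaging confirmation of internal derangement (ligament/articular/bony injury"). Clinical and imaging findings are joined by 'and'; the imaging modality is not named.
- Section 5.1, criterion 2: "Wrist pathology based on clinical examination/imaging studies undergoing wrist arthroscopy for further evaluation/treatment". The slash can be read as and/or.
- Section 5.4: "Patients with clinically diagnosed wrist pathology undergoing wrist arthroscopy will be identified by the attending physician". Imaging is not mentioned.

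On MRI, section 3.2 says "The MRI is standard of care for evaluation of ligamentous wrist pathology" and then "It will not be mandated as part of the protocol". The comparison set is fixed in section 7.1.1: "Patients with pre-operative MRIs with a corresponding radiology report will be compared to arthroscopic findings". Section 10.3.3 lists the endpoint as "Correlation between pre-operative MRI findings and arthroscopic findings" and says that secondary endpoints will be summarised as incidence or percentage. It names no coefficient, no unit of analysis (wrist or structure) and no handling of selection. Section 7.1.1 does list ten structures to be inspected in every wrist.

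**The concern.** Arthroscopy is the reference, so MRI can be checked only in wrists that were operated on. If a positive image makes surgery more likely, MRI-negative wrists are under-represented among those checked. This is partial verification. Missed lesions drop out of the denominator of sensitivity, and correctly negative wrists drop out of the numerator of specificity.

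A single percentage from such a cohort partly describes how patients were chosen for surgery. A reader could take it as a measure of how well MRI detects wrist lesions, or set it beside the MRI sensitivity of 0.70 that section 10.4 uses for the sample size. Neither use would be sound. The three descriptions of entry make this harder to judge, because they imply different amounts of imaging-based selection.

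**Working it through.** **The plan's own figures.** No sample size or precision is given for the MRI objective. Section 10.4 supplies the two inputs used here: MRI sensitivity 0.70 and prevalence 0.90. Its calculation reproduces. An exact two-sided binomial test of 0.70 against 0.90 with 31 injured wrists rejects at 27 or more (or 16 or fewer), with alpha 0.0478 and power 0.807, as in the table row for that contrast; 31/0.90 = 34.4, printed as 34.

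**Inputs for the selection check**

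- From section 10.4: prevalence p = 0.90, MRI sensitivity Se = 0.70.
- Assumed, not in the documents: MRI specificity Sp = 0.80 (varied from 0.60 to 0.95); referral depends on the MRI result only; r, the chance that an MRI-negative wrist reaches arthroscopy relative to an MRI-positive one.

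**Cells among operated wrists, before rescaling**

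- MRI+, lesion: p·Se = 0.90 × 0.70 = 0.63
- MRI−, lesion: r·p·(1 − Se) = 0.27r
- MRI+, no lesion: (1 − p)(1 − Sp) = 0.02
- MRI−, no lesion: r·(1 − p)·Sp = 0.08r

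**Formulas**

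- Apparent sensitivity = 0.63/(0.63 + 0.27r)
- Apparent specificity = 0.08r/(0.08r + 0.02)
- Agreement = (0.63 + 0.08r)/(0.65 + 0.35r)

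At r = 0.5 these are 0.63/0.765 = 0.82, 0.04/0.06 = 0.67 and 0.67/0.825 = 0.81. For kappa at r = 0.5, the MRI-positive share is 0.65/0.825 = 0.788 and the lesion share is 0.765/0.825 = 0.927. Chance agreement is 0.788 × 0.927 + 0.212 × 0.073 = 0.746, so kappa = (0.812 − 0.746)/(1 − 0.746) = 0.26.

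| r | Sensitivity | Specificity | Agreement | Kappa | Phi |
|---|---|---|---|---|---|
| 1 | 0.70 | 0.80 | 0.71 | 0.24 | 0.31 |
| 0.5 | 0.82 | 0.67 | 0.81 | 0.26 | 0.31 |
| 0.25 | 0.90 | 0.50 | 0.88 | 0.26 | 0.28 |
| 0 | 1.00 | 0.00 | 0.97 | 0 | undefined |

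The last row is the limiting case in which every compared wrist is MRI-positive. Agreement there is simply the positive predictive value, 0.63/0.65.

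**Sensitivity to the assumptions.** At 90% prevalence, moving from r = 1 to r = 0.5 raises agreement from 0.69 to 0.79 with Sp = 0.60, and from 0.73 to 0.83 with Sp = 0.95. The rise depends on high prevalence: with p = 0.50 and Sp = 0.60, both assumed, agreement goes from 0.650 to 0.645.

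**Numbers of wrists.** If all 34 had an MRI and there were no selection, 0.35 × 34 ≈ 12 would be MRI-negative, and only 0.10 × 34 = 3.4 would be free of injury. A per-wrist specificity would be very imprecise even without selection.

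**The case against.** The strongest reply has four parts.

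- **The Summary row is not an entry rule.** Eligibility is set in section 5.1, and sections 7.2.1 and 7.2.2 send the investigator to the eligibility criteria. Section 5.1 can be met on examination alone. This stands. A reader might infer that the Summary makes imaging confirmation compulsory, but the documents show an inconsistency, not a requirement.
- **Imaging is not said to be MRI, and MRI is not mandated.** This also stands. A reader might go on to infer that every wrist is MRI-positive at entry, so that the MRI question cannot be answered per wrist. That needs the confirming imaging to be MRI and positive in every compared wrist. MRI is called usual care for ligament injury and section 10.4 counts on 31 ligament injuries, so MRI will often be the imaging used. Still, a wrist confirmed by another modality could be MRI-negative.
- **The endpoint is called a correlation, and kappa and phi barely move under partial selection.** Correct. Selection does not push every measure towards agreement: specificity falls, and at full selection kappa is 0 and phi is undefined. But the only summary that section 10.3.3 specifies for this endpoint is a percentage, and that is the kind of figure that does rise.
- **Only operated wrists can ever be verified, and section 10.1 promises a formal SAP.** The limitation is inherent, and the plan never calls the wrists unselected. A later SAP can define the analysis. It cannot recover why a wrist was operated on if that was not recorded, because section 13.5 removes the key linking data to medical records once collection ends.

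**Conclusion.** The concern holds in a limited form. The Protocol Summary and sections 5.1 and 5.4 describe the cohort differently and need reconciling. Because imaging can contribute to the decision to operate and only operated wrists with an MRI report are compared, a percent-agreement or sensitivity summary is inflated at the plan's 90% prevalence. With halved referral of MRI-negative wrists, the inflation is about 0.10 in agreement and 0.12 in sensitivity, with a loss of about 0.13 in apparent specificity and almost no change in kappa.

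These sizes rest on an assumed specificity, on referral driven by MRI alone and on a value of r that the documents do not give; clinical findings also enter the decision, so the true effect could be smaller. The comparison would be uninformative per wrist only in the limiting case r = 0, which the documents do not establish. The objective is secondary, and nothing here bears on the primary comparison of NanoScope with the conventional arthroscope.

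**What to change.** 1. Bring the Key Procedures row of the Protocol Summary and section 5.4 into line with section 5.1.
2. Record from the chart, while the linking key still exists, whether and when MRI was done and which structure or structures prompted surgery.
3. In sections 7.1.1 and 10.3.3, compare MRI with arthroscopy by structure over the ten listed structures, allowing for clustering within wrist. Report the structure(s) that prompted surgery separately from the rest. The rest are inspected in every operated wrist whatever MRI showed of them, so the split reduces selection. It does not remove it, because they still come from wrists chosen for surgery, and the report should say so.
4. Describe the result as concordance among operated wrists with an MRI, not as MRI accuracy.

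The cost is some protocol wording, one or two extra case report form fields and a narrower claim about MRI. No patients or procedures are added.
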